**Sample size and calculated power**

*Justification of power calculation*

A total of 720 women will be recruited. In order to be able to show a difference of 80 percent in IUC usage in the immediate insertion group at 6 months post insertion compared to 60 percent use in the delayed group with a power of 90 percent and an alpha of 0.05 we would need to randomize 109 women in each group.

If close to 100 percent of women receive the IUC in the immediate group and there is an expulsion rate of maximum 15 percent (immediate post placental insertion after delivery has expulsion rates of 15 percent) and some women have the IUC removed a use of approximately 80 percent could be expected in the immediate group. In the delayed group fewer women are estimated to come for insertion and the expulsion rate is estimated at 5 percent.

We will stratify women in three gestational age categories ( $\leq 9$  weeks+0 days, 9weeks +1 day  $\leq 12$  weeks+0 days, and  $>12$  weeks) to make study data more internationally applicable. We will compensate for surgical procedures due to incomplete abortions and prolonged bleeding which is estimated to be needed in approximately 3-5 percent (13). We will also compensate for a 15 percent loss to follow up which is commonly seen in studies in abortion. Thus, we will randomize 240 women in each gestational strata (total 720 women). Analysis will be presented as intention to treat for all randomized women as well as per protocol for women completing the 6 month follow up (see analysis plan). Follow up at 3, 6 and 12 months will be performed by telephone/email. In women who do not attend FU electronic patient records will be searched for main and secondary outcomes (safety, pregnancy, abortion).

Women will be recruited at several sites in Sweden. Recruitment (numbers) is not expected to be equal at each site but this will be considered in the statistical analysis.

Statistical advice from statistician [name] (adjunct professor and professional medical statistician) has been sought for study design, power calculation, and analysis plan.

Randomization:

The randomization ratio between intervention and control group will be 1:1 in permuted blocks of 4-8 in three strata and per site.

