Randomization will be performed by the midwife in the family planning/ abortion clinic at the time of intake of mifepristone after the patient has been judged eligible for participation and has signed informed consent in the presence of the attending physician. Allocation to intervention or control will be performed via opening of opaque sealed envelopes in consecutive order. Each site will have a separate randomization sequence. All women will be identified through a patient log with name and Swedish personal identification number and the randomization number. The randomization number will be used on all paper and eCRFs. The study will for practical and ethical reasons not be blinded. The medical abortion will be performed according to the Swedish national guidelines.

Choice of study design:

The project will be performed as a randomized, controlled, multicenter superiority trial. It is known that sociodemographic factors such as parity and age may influence the choice of contraception and the rate of continued use. The rate of expulsion may be influenced by parity and gestational length. To eliminate these confounders the randomized design is superior. Many of the factors studied such as the primary outcome are objective and should not be affected by the non-blinded design. It is not deemed feasible to do a single blinded study where the health care provider would be blinded to the insertion time as the women with immediate insertion will likely be bleeding more than the women with delayed insertion. The women with immediate insertion will also have an open outer cervical os. Therefore, the health care provider would likely be affected by these findings at the IUC insertion.

**Primary outcome** will be the use of IUC at 6 months follow up. A difference of 20 percent between the study groups (immediate versus delayed insertion) will be considered as clinically significant (please see justification for power calculation).

**Secondary outcomes** include the rate of IUC inserted, rate of expulsion, pain at insertion, bleeding, reasons for non-insertion of IUC, IUC use, complications, acceptability, pregnancies and abortions evaluated at 3 and 6 months follow up and annually up to five years.

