### **Variables and measures**

Primary outcome measure:

- Use of IUC at 6 months post insertion evaluated by telephone follow-up and through patient records. This will be evaluated as the proportion of women in each gestational strata (use of IUC versus no use of IUC).

Secondary outcome measures:

- Difference in the proportion of women who successfully have the IUC inserted (success versus failure),
- Expulsion rate during 12 months following insertion in both groups evaluated by telephone/email follow up at 3, 6 and 12 months post abortion (complete, partial or no expulsion. The exact day of expulsion will be noted to determine the risk of expulsion as a function of time post insertion),

- Continued use of IUC at 3, 6 and 12 months post insertion evaluated by telephone follow-up (continued use/voluntary discontinued use, involuntary discontinued use including expulsions etc) reasons for discontinuation will be recorded and subsequent use of other contraceptive methods will be noted)
- Ease of insertion according to health care provider (judged as very easy, moderately-, or very difficult)
- pain at time of insertion (women will indicate the pain before insertion, at placement of tenaculum, sound and IUC by putting a vertical mark on a 10 cm long horizontal line with a Visual Analogue Scale (VAS) from 0, indicating no pain to 10 indicating worst imaginable pain. Result will be noted in millimeters and entered into case report forms).
- Post-abortion bleeding (number of days of fresh bleeding and spotting after the abortion)
- Reasons for non-attempted insertion of IUC (change of mind, heavy bleeding, not coming for insertion, staff being unavailable etc),
- Complications (adverse events (AE) and serious AE) bleeding requiring any treatment, uterine perforations and cervical tears, infection requiring treatment with antibiotics, hospitalization for any reason, surgical procedures due to heavy bleeding, incomplete abortions, prolonged bleeding or patient request,
- Pregnancies occurring during the 12 month follow-up (planned and unplanned, wanted and unwanted, pregnancy outcomes- ectopic, miscarriage, abortion, molar, kept pregnancy),
- Acceptability of immediate and delayed insertion of IUC by asking women if they would recommend the procedure to a friend (yes/no, asked at the time of insertion and at the 3, 6 and 12 month follow up),
- Acceptability of IUC as post abortion contraception- evaluated as above,

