## **17 Statistical considerations - Sample size**

### ***17.1 Justification of power calculation***

A total of 720 women will be recruited. In order to be able to show a difference of 80 percent in IUC usage in the immediate insertion group at 6 months post insertion compared to 60 percent use in the delayed group with a power of 90 percent and an alpha of 0.05 we would need to randomize 109 women in each group. If close to 100 percent of women receive the IUC in the immediate group and there is an expulsion rate of maximum 15 percent (immediate post placental insertion after delivery has expulsion rates of 15 percent) and some women have the IUC removed a use of approximately 80 percent could be expected in the immediate group. In the delayed group fewer women are estimated to come for insertion and the expulsion rate is estimated at 5 percent.

We will stratify women in three gestational age categories ( $\leq 9$  weeks+0 days, 9weeks +1 day  $\leq 12$  weeks+0 days, and  $>12$  weeks) to make study data more internationally applicable. We will compensate for surgical procedures due to incomplete abortions and prolonged bleeding which is estimated to be needed in approximately 3-5 percent (13). We will also compensate for a 15 percent loss to follow up which is commonly seen in studies in abortion. Thus, we will randomize 240 women in each gestational strata (total 720 women). Analysis will be presented as intention to treat for all randomized women as well as per protocol for women completing the 6 month follow up (see analysis plan). Follow up at 3, 6 and 12 months will be performed by telephone/email. In women who does not attend FU electronic patient records will be searched for main and secondary outcomes (safety, pregnancy, abortion).

- Primary outcome:

The primary outcome is the difference in women with IUC use at 6 months between the two groups (immediate and delayed insertion). The results will be analyzed by Fisher's exact test. A sensitivity analysis will be performed using logistic regression taking center, parity and age into account.

- Analysis populations

The main analysis population for primary outcome will be a modified intention to treat (mITT). This population is all randomized women, with medical abortion, and follow up for main outcome recorded at 6 months. Hence, also women with no insertion and women experiencing expulsion are included in this mITT.

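### The protocol does not say whether the primary Fisher test is pooled or run per gestational stratum; if pooled it is mildly conservative, and the logistic sensitivity model omits gestational stratum

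*Protocol*

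**What the plan says.** Section 5, under Sample size and calculated power, fixes the allocation: "The randomization ratio between intervention and control group will be 1:1 in permuted blocks of 4-8 in three strata and per site". The three strata are gestational age up to 9+0 weeks, 9+1 to 12+0 weeks, and over 12 weeks. Under Choice of study design, the same section states: "The rate of expulsion may be influenced by parity and gestational length".

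Section 17.1 compares IUC use at 6 months between the immediate and delayed groups and names the test: "The results will be analyzed by Fisher's exact test". No stratification is mentioned. The only adjusted analysis follows: "A sensitivity analysis will be performed using logistic regression taking center, parity and age into account".

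Two other statements point towards an analysis within strata. Section 5, Variables and measures, says of the primary outcome: "This will be evaluated as the proportion of women in each gestational strata (use of IUC versus no use of IUC". Sections 5 and 17.1 also derive 109 women per group and then randomise 240 women in each stratum, 720 in all, so the power calculation is applied stratum by stratum.

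On site, section 5 says: "Recruitment (numbers) is not expected to be equal at each site but this will be considered in the statistical analysis".

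**The concern.** An analysis normally respects the factors used to stratify randomisation. If a stratification factor predicts the outcome and the test ignores it, balance between arms makes the observed difference less variable than the test assumes. The test is then conservative: it rejects too rarely under the null and loses some power. Fisher's exact test is already conservative because it is discrete, so the two effects add.

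The protocol gives its own reason to expect gestational age to matter. It says gestational length may influence expulsion, and the WHO table reproduced in section 3.1 reports more expulsions after second-trimester than first-trimester abortion. An expelled device that is not replaced counts as non-use at 6 months. Yet the logistic model keeps parity, the other factor named for expulsion, and leaves out gestational stratum, which is also a randomisation factor.

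Beneath this is a question of definition. One pooled test on 720 women and three separate tests on 240 women each are different primary analyses, and the protocol supports both readings.

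**Working it through.** **1. The plan's own figure.** Inputs from section 17.1: 80% versus 60%, power 90%, alpha 0.05. Sidedness is not stated. The two-sided formula with pooled variance under the null is

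n = [z(0.975)·√(2·p̄·(1−p̄)) + z(0.90)·√(p1(1−p1) + p2(1−p2))]² / (p1−p2)²

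With p̄ = 0.70: [1.960·√0.42 + 1.282·√0.40]² / 0.04 = (1.270 + 0.811)² / 0.04 ≈ 108.2, which rounds up to 109. The stated figure is reproduced. The calculation concerns a single comparison, and the protocol applies it to each stratum.

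**2. Numbers analysed.** 240 per stratum is 120 per arm. After the stated 15% loss: 120 × 0.85 = 102. After a further 5% for surgical procedures (upper end of the stated 3-5%): 102 × 0.95 ≈ 97. Pooled over three strata: 3 × 97 = 291 per arm.

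**3. Pooled reading: why ignoring strata is conservative.** With equal strata and balanced arms, the pooled test uses the variance p̄(1−p̄), while the true null variance is the average of p(1−p) within strata. For stratum rates of 80/60/40% (assumed; the protocol gives none):

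- pooled: 0.60 × 0.40 = 0.240
- within strata: (0.16 + 0.24 + 0.24)/3 = 0.213
- ratio: 0.889, so the effective critical value is 1.960/√0.889 = 2.079 and the size is about 3.8% before any effect of Fisher's discreteness.

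For 70/60/50% the ratio is 0.233/0.240 = 0.972, and the size is about 4.7%.

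**4. Pooled reading: simulation.** 100,000 trials per scenario, 97 per arm per stratum, two-sided 5%. The uncorrected Pearson test is also unstratified, so the step from Fisher to Pearson shows the cost of Fisher's discreteness, and the step from Pearson to Cochran-Mantel-Haenszel (CMH) shows the cost of ignoring strata.

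| Control rates by stratum (assumed) | True difference | Fisher | Pearson | CMH |
|---|---|---|---|---|
| 60/60/60% | 0 | 4.0% | 4.9% | 4.9% |
| 65/60/55% | 0 | 3.9% | 4.8% | 4.9% |
| 70/60/50% | 0 | 3.7% | 4.6% | 5.1% |
| 80/60/40% | 0 | 2.9% | 3.7% | 5.0% |
| 60/60/60% | 10 points | 68.8% | 71.9% | 71.8% |
| 65/60/55% | 10 points | 68.9% | 71.9% | 72.0% |
| 70/60/50% | 10 points | 69.1% | 72.2% | 72.9% |
| 80/60/40% | 10 points | 69.9% | 73.0% | 76.8% |
| all four | 20 points | over 99.9% | over 99.9% | over 99.9% |

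At 10 points, Fisher loses about 3.0, 3.1, 3.8 and 6.9 points to CMH. Some 3 points of each gap come from Fisher's discreteness. Ignoring strata adds nothing with flat strata, 0.7 points (72.9 − 72.2) at 70/60/50%, and 3.8 points (76.8 − 73.0) at 80/60/40%.

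**5. Second set of assumptions.** 20,000 trials, 102 per arm per stratum. Null at 80/70/50%: Fisher 3.5%, CMH 4.8%. Power for a 10-point difference, Fisher against CMH:

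- 85/75/55% versus 75/65/45% (spread 30 points): 72.7% and 77.8%, a gap of 5.1 points
- 90/75/45% versus 80/65/35% (spread 45 points): 72.6% and 80.5%, a gap of 7.9 points
- flat strata: 74.2% and 76.7%, a gap of 2.5 points

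**6. Per-stratum reading.** Gestational age is then held fixed within each test, so steps 3 to 5 do not apply. What remains is Fisher's own cost at 80% versus 60%, by exact enumeration: 87.6% power at 109 per arm (Pearson 90.5%) and 83.4% at 97 per arm (Pearson 87.0%). This comes from the choice of test and has nothing to do with ignored gestational strata.

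**The case against.** A reader might infer that the primary test certainly ignores both stratification factors. The protocol does not support that. The statement under Variables and measures and the per-stratum sizing allow one Fisher test in each stratum, which conditions on gestational age. This stands, and it is why the two sections need reconciling before any test is replaced.

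A reader might also infer that the promise to consider site is broken. It is not. The promise refers to the statistical analysis in general, and the logistic model includes centre.

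The harm is limited. The error is on the conservative side, and the losses appear at 10 points, half the difference the protocol calls clinically significant. About 3 points of each loss belong to Fisher's test itself. The larger losses need wide spreads in use between strata, whereas the protocol says only that gestational length may influence expulsion. With 65/60/55% almost nothing is lost by ignoring strata. All of this stands and sets the severity.

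It could be argued that age in the logistic model means gestational age. That is unlikely, because Choice of study design pairs parity with age as sociodemographic factors and names gestational length separately. The wording should still say maternal age.

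The absence of a stated confidence interval or permutation scheme is no defect here. The protocol does not fix these details, and they can be left to the statistical analysis plan.

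**Conclusion.** The point holds and is minor. Two things are certain from the text: the protocol does not settle whether the primary Fisher test is pooled or per stratum, and the logistic sensitivity model omits gestational stratum although it is a randomisation factor that the protocol itself thinks may be prognostic.

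If the test is pooled, it is mildly conservative. Its true size is about 4% from discreteness alone and about 3-4% with assumed prognostic strata, against about 5% for CMH. At a 10-point difference power is about 3 points lower with flat strata and 4-8 points lower with spreads of 20-45 points. These figures rest on three equal strata, 97 or 102 women analysed per arm per stratum, and stratum rates that are assumptions.

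A reader might infer that the primary result would be invalid or the trial underpowered for its planned effect. Neither follows from ignoring strata: there is no type I error inflation, and the pooled test has over 99% power at 20 points with or without stratification.

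**What to change.** 1. State in section 17.1 whether the primary test is pooled over gestational strata or run in each stratum, and bring Variables and measures in section 5 into line.
2. If pooled, replace Fisher's test for the primary outcome with a Cochran-Mantel-Haenszel test stratified by the three gestational categories, and report the Mantel-Haenszel risk difference.
3. On either reading, add gestational stratum to the logistic model alongside centre, parity and age, and specify maternal age.

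The cost is wording only, since the strata are already recorded at randomisation. Changing the primary test may need a protocol amendment under section 16.1.

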### ***4.4 Variables***

#### **4.4.1 Efficacy, acceptability:**

- Difference in the proportion of women who successfully have the IUC inserted (success versus failure),
- Continued use of IUC at 3 and 12 months post insertion evaluated by telephone/email follow-up (continued use/voluntary discontinued use, involuntary discontinued use including expulsions etc) reasons for discontinuation will be recorded and subsequent use of other contraceptive methods will be noted)
- Ease of insertion according to health care provider (judged as very easy, easy, moderately, or very difficult)
- pain at time of insertion (women will indicate the pain before insertion, at placement of tenaculum, sound and IUC by putting a vertical mark on a 10 cm long horizontal line with

a Visual Analogue Scale (VAS) from 0, indicating no pain to 10 indicating worst imaginable pain. Result will be noted in millimeters and entered into case report forms).

- Post-abortion bleeding (number of days of fresh bleeding and spotting after the abortion)
- Reasons for non-attempted insertion of IUC (change of mind, heavy bleeding, not coming for insertion, staff being unavailable etc),
- Pregnancies occurring during the 12 month follow-up (planned and unplanned, wanted and unwanted, pregnancy outcomes- ectopic, miscarriage, abortion, molar, kept pregnancy),
- Acceptability of immediate and delayed insertion of IUC by asking women if they would recommend the procedure to a friend (yes/no, asked at the time of insertion and at the 3, 6 and 12 month follow up),
- Acceptability of IUC as post abortion contraception- evaluated as above,

[figure not shown]

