A sensitivity analysis will be performed on a strict ITT-population consisting of all randomized women having had medical abortion. In this analysis it is required to impute the outcome for women lost to follow up.

- Secondary efficacy outcomes:

1. Abortion rate as difference in proportion of individuals in each group at 3, 6 and 12 months,

Since both the primary outcome and this outcome involve data from different time-points several tests can be performed. In order to reduce the risk for type-I error each research question will be addressed with a global test including all available time-points first, before studying individual time-points. The data has a repeated-measure structure with a dichotomous outcome and most likely more observations available for early time-point compared to later time-points. To properly handle this data-structure we will use a multivariate permutation test based on a Fisher's combination function of individual  $p$ -values from time-specific tests (Fisher's exact test). If this global test is non-significant no individual time-points will be considered significant

2. Difference in the proportion of women who successfully have the IUC inserted (success versus failure),

Analyzed by Fisher's exact test.

- Secondary safety outcomes

1. rate of complications such as expulsions, perforations, infections. (Fisher's exact test)
2. Length of post abortion bleeding (difference in mean number of days in groups and per IUC use (hormonal/copper). Analyzed by T-test or Mann-Whitney U-test depending on the observed distribution (normal or skewed).
3. Pain at insertion on a VAS. Analyzed by Student's t-test

These secondary analyses concern safety where it is not sensible to adjust for multiple testing. The adjustments (with e.g. Bonferroni) increases the risk for type-II errors. As safety issues are very important we do not wish to increase the risk for type-II errors. Moreover, the analyses are listed under secondary endpoints so this implies that the results should be interpreted with more caution compared to the primary result.

- Secondary acceptability outcomes
  1. preferred method: immediate or delayed and if they would recommend their timing of insertion to a friend (yes/no). Analyzed by multivariate logistic regression with group, demographic variables and type of IUC (hormonal/copper) as explanatory variables.

Secondary analyses will be performed on all women with available data.

- Interim analysis:

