In the interim analysis no analyses of efficacy will be performed. Hence there is no need to adjust any statistical test due to the interim analysis.

All test will be performed at the 5% significance level. The analysis plan has been developed by the principal investigator and [name], adjunct professor in medical statistics, Statisticon AB.

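### Length of post-abortion bleeding is defined as a difference in mean days, but the test is switched on the observed distribution, and the branch likely to apply does not test a mean difference

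*Protocol*

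**What the plan says.** The protocol lists the variable in section 4.4.1 as "Post-abortion bleeding (number of days of fresh bleeding and spotting after the abortion"); the Synopsis and sections 5 and 11 list it the same way. None of these places names a summary measure.

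The summary measure appears only in section 17.1, second item under the secondary safety outcomes: "Length of post abortion bleeding (difference in mean number of days in groups and per IUC use (hormonal/copper"). The same item continues: "Analyzed by T-test or Mann-Whitney U-test depending on the observed distribution (normal or skewed").

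Three neighbouring statements bear on this:
- The next item fixes a single test: "Pain at insertion on a VAS. Analyzed by Student's t-test".
- The analysis set is given as: "Secondary analyses will be performed on all women with available data".
- The level is given as: "All test will be performed at the 5% significance level". Section 17.1 also says that the safety outcomes are not adjusted for multiplicity, because the authors do not want to raise the type II error risk there.

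**The concern.** The item names one quantity, a difference in means, and then lets the data choose between two tests of different hypotheses. The t-test addresses the difference in means. Mann-Whitney addresses whether a woman in one arm tends to bleed longer than a woman in the other. The two questions coincide when the arms differ only by a shift. They can part when the spread or the tail differs as well.

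The skewed branch is the one likely to apply, because the variable is a count of days that cannot fall below zero. On that branch the reported p-value need not belong to the reported mean difference. The trial could then declare a difference in bleeding when mean days are equal. It could also miss a real difference in mean days caused by a minority of long bleeds. The second error is the one section 17.1 says it wants to avoid for safety outcomes.

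**Working it through.** **The plan's own figure.** The protocol gives no number for bleeding. Its only sample size statement is for the primary outcome: "with a power of 90 percent and an alpha of 0.05 we would need to randomize 109 women in each group", for 80% vs 60%. With two-sided 5% and pooled variance, n = [1.960·√(2·0.7·0.3) + 1.2816·√(0.8·0.2 + 0.6·0.4)]² / 0.2² = (1.270 + 0.811)² / 0.04 ≈ 108.2, so 109. The figure reproduces, and it has no bearing on this point.

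**Inputs from the protocol.** 720 women randomized 1:1 gives 360 per arm. Less the 15% loss allowed for, 360 × 0.85 = 306 per arm. The level is 5%, taken as two-sided.

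**Inputs assumed.** The protocol gives no mean, SD or shape for bleeding days. Two right-skewed families were used, with values rounded to whole days:
- Gamma with mean m and SD s: shape (m/s)², scale s²/m.
- Lognormal with median 12 and log-SD σ: mean = 12·exp(σ²/2). For σ = 0.5 this is 12 × 1.133 = 13.6; for σ = 0.8 it is 12 × 1.377 = 16.5.

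**Check.** Thousands of simulated trials per scenario, 306 per arm. The table shows the share of trials with p < 0.05.

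| Assumed truth | Mann-Whitney | Welch |
|---|---|---|
| Identical gamma distributions | about 5% | about 5% |
| Equal means 14, SD 9 vs 10 | about 8% to 10% | about 5% |
| Equal means 14, SD 8 vs 10 | about 21% | about 5% |
| Equal means 14, SD 7 vs 12 | about 81% | about 5% |
| Equal medians 12, means 13.6 vs 16.5 | about 6% | about 89% |
| Means 14 vs 16.5, SD 8 vs 10 | about 83% | about 92% |
| Means 14 vs 16.5, SD 8 vs 12 | about 35% | about 87% |

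Repeated runs agree to within a few percentage points.

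**Why this happens.** In the fourth row both means are 14, but the gamma medians are about 12.9 (SD 7) and 10.8 (SD 12). A woman from the narrower arm has the longer bleed with probability about 0.57. Mann-Whitney correctly detects that ordering, but the ordering is not a mean difference.

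**Which branch is taken.** The protocol does not say how skewness is judged. With a Shapiro-Wilk test as an assumed switch, skewed data of this kind go to Mann-Whitney in essentially every trial, so the two-step rule inherits the Mann-Whitney column.

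**Does skewness force the switch?** At these sizes it does not. When the means are equal, the mean-based tests stay at about 5% to 6% with 100 to 306 women per arm.

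**Smaller comparisons.** At 100 per arm the pattern persists but is weaker. In the equal-medians scenario Mann-Whitney rejects in about 6% of trials and Welch in about 38%. The hormonal/copper comparison was not simulated, since the protocol does not give its group sizes.

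**The case against.** The best counter-argument is that the discrepancy depends on how far the shapes differ, and the protocol says nothing about that. Its one relevant remark, in section 3.1, is that early LNG-IUS uptake may reduce post-abortion bleeding, which points to a change in level. When level and spread move together, both tests usually find the difference (83% vs 92%). When the spreads are close, the excess rejection is only a few percentage points. This stands: the large percentages belong to scenarios in which the spread changes strongly and out of step with the mean, and they are not predictions for this trial.

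It also stands that for skewed durations a rank-based summary is defensible. The defect is the mismatch between quantity and test, not the use of Mann-Whitney as such.

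Two stronger readings are tempting, and the protocol does not support them:
- A reader might infer that the open-label design lets the analysts pick the favourable test. The stated trigger is the shape of the distribution, not the treatment effect or the p-value, so the text gives little ground for this.
- A reader might count the missing criterion for skewness as a defect of its own. That detail is commonly left to an analysis plan, and section 17.1 refers to one that is not at hand.

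What the objection does not remove is that the protocol itself fixes both the mean difference and the switching rule, and nothing elsewhere in it reconciles them.

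**Conclusion.** The point holds as an inconsistency between a stated quantity and a stated test. On the branch likely to apply, the p-value does not answer the question about mean days unless the arms differ by a pure shift.

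The possible size runs from nothing (identical shapes) through a few percentage points (SD 9 vs 10) to a serious error in either direction (SD 7 vs 12, or equal medians with means about three days apart). It rests on assumed gamma and lognormal shapes, 306 women per arm and a two-sided 5% level.

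The consequence is confined to one unadjusted secondary safety outcome, a class that section 17.1 already says should be read more cautiously than the primary result. A reader might infer that the trial's main conclusion or its safety stopping is at risk. Neither is: the primary outcome, the sample size and the stopping rule (expulsion and acceptability) do not use bleeding duration. The change is worth making because it is cheap and the outcome is a named safety outcome.

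**What to change.** In section 17.1, delete the choice that depends on the observed distribution and prespecify one analysis of the stated quantity. That analysis is the difference in mean days with a Welch t-test and 95% confidence interval, with a bootstrap interval as a check. Apply it both to the comparison of arms and to the hormonal/copper comparison. Report medians alongside, and keep Mann-Whitney as supportive only.

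If the sponsor prefers a rank-based analysis, the coherent alternative is to restate the quantity to match it, for example as a location shift or as the probability of longer bleeding, and to fix that one test in advance.

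The cost is one sentence, with no effect on sample size or data collection. The downside of the first option is that the mean is more sensitive to a few very long durations; the medians and the supportive test will show whether that has happened.
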